7.3.7 Cycle 3 and Beyond, Day 1 (± 72 hours)

Regorafenib may not start until the patient's hematologic, liver and renal functions have been reconfirmed as eligible according to the Section 3.1 by the Investigator. Therefore, the regorafenib cycle starts on the day that treatment begins. If liver function toxicities are present, patient may be rechecked weekly for 2 additional weeks. Those patients with persistent liver function toxicities after this time will come off study, but will be followed until resolution.

- Physical examination, weight, and vital signs
- BP
- ECOG PS
- AE assessment
- Concomitant medication review
- CBC
- CMP
- PT/PTT/INR (for patients receiving Coumadin therapy)
- Biomarker blood sample collection (Day 30 (pre-dose) following SIR-Spheres treatment)
- CEA tumor marker

7.3.8 Cycle 3 and Beyond, Day 15

- PT/PTT/INR (for patients receiving Coumadin therapy)

7.4 Study Treatment Assessments – COHORT 2

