3. STUDY PATIENT POPULATION AND DISCONTINUATION

3.1 Inclusion Criteria

Patients must meet the following criteria in order to be included in the research study:

1. Histologically confirmed metastatic adenocarcinoma of the colon or rectum.
2. Patients who have been previously treated with or are not candidates for fluorouracil, oxaliplatin, irinotecan, and if Kras wild-type, anti EGFR therapy
3. Considered an appropriate candidate for regorafenib therapy.
4. Measurable disease as measured by Response Evaluation Criteria in Solid Tumors (RECIST) version 1.1 (Appendix C).
5. Measurable computed tomography (CT) scan evidence of liver metastases which are not treatable by surgical resection or local ablation with curative intent at the time of study entry.
6. Eastern Cooperative Oncology Group (ECOG) Performance Status (PS) score of 0-1 (Appendix D).
7. Adequate hematologic function defined as:
 - Absolute neutrophil count (ANC) $\geq 1500/\mu\text{L}$
 - Hemoglobin (Hgb) $\geq 9 \text{ g/dL}$ (pre-enrollment transfusion allowed)
 - Platelets $\geq 75,000/\mu\text{L}$
8. Adequate liver function defined as:
 - Alanine aminotransferase (ALT) and aspartate aminotransferase (AST) $\leq 2.5 \times$ the upper limit of normal (ULN) or $<5 \times$ ULN if due to hepatic metastases
 - Total bilirubin $\leq 1.5 \times$ ULN (unless the patient has Grade 1 bilirubin elevation due to Gilbert's disease or a similar syndrome involving slow conjugation of bilirubin)
9. Adequate renal function defined as serum creatinine $\leq 1.5 \text{ mg/dL}$ (133 $\mu\text{mol/L}$) OR calculated creatinine clearance $\geq 50 \text{ mL/min}$.
10. Male patients with female partners of childbearing potential and female patients of childbearing potential are required to use two forms of acceptable contraception, including one barrier method, during their participation in the study and for 30 days following last dose. Male patients must also refrain from donating sperm during their participation in the study (Appendix E).
11. Life expectancy ≥ 3 months.
12. Age ≥ 18 years.
13. Ability to understand the nature of this study and give written informed consent.

CONFIDENTIAL

STUDY DEVICE: SIR-Spheres®

SCRI INNOVATIONS STUDY NUMBER: GI 189

DATE OF ORIGINAL PROTOCOL: 16 December 2013

Date of Amendment #1: 15 April 2014

Version 2.0

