6.2 Regorafenib Dose Modifications for Non-Hematologic Toxicity

6.2.1 Regorafenib Dose Modifications for Abnormal Liver Function Tests

Regorafenib has been associated with severe drug-induced liver injury with fatal outcome in previous studies. Liver function tests (LFTs) will be monitored during study treatment as described in **Error! Reference source not found.** Appendix A and **Error! Reference source not found.** Appendix B. Dose modifications for regorafenib are recorded in Table 3 below.

Table 3 Regorafenib Dose Modifications for Abnormal Liver Function Tests

Toxicity	Regorafenib Dose
Baseline - Grade 1 And Recurrence OR Baseline Grade 1 – Grade 2 And Recurrence	Treat on time and check AST, ALT and bilirubin 2x/week for 2 weeks followed by weekly assessments for at least 4 weeks.
Baseline - Grade 2	Hold dose until \leq Grade 1 and check AST, ALT and bilirubin 2x/week. Resume regorafenib at 1 lower dose level and check AST, ALT, bilirubin 2x/week for 2 weeks followed by weekly assessments for at least 4 weeks. ^a
Recurrence of Baseline - Grade 2	Discontinue regorafenib ^b .
Baseline Any Grade-Grade 3	Hold dose until \leq Grade 1 for baseline - Grade 1 OR until Grade 2 if baseline was Grade 2.

CONFIDENTIAL

STUDY DEVICE: SIR-Spheres®

SCRI INNOVATIONS STUDY NUMBER: GI 189

DATE OF ORIGINAL PROTOCOL: 16 December 2013

Version 2.0

Date of Amendment #1: 15 April 2014

	Check AST, ALT and bilirubin 2x/week.
	Resume regorafenib at 1 lower dose level and check AST, ALT, bilirubin 2x/week for 2 weeks followed by weekly assessments for at least 4 weeks. ^a
	Note: If ALT or AST >8 x ULN with a concomitant rise in bilirubin (of any degree) compared to previous bilirubin values, consider permanent discontinuation at the first occurrence ^b .
Recurrence of Baseline Any Grade-Grade 3	Discontinue regorafenib ^b .
Baseline Any Grade-Grade 4	Discontinue regorafenib ^b

^a If all values remain stable for 2 full cycles, dose re-escalation may be considered at the discretion of the investigator. After re-escalation AST, ALT, and bilirubin should be checked 2x/week for 2 weeks, followed by weekly assessments for at least 4 weeks.

^b In case of discontinuation, AST, ALT, and bilirubin should be checked 2x/week for 2 weeks, followed by weekly assessments until recovery to baseline.

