7.4.4 Cycle 2, Day 1 (± 72 hours)

Regorafenib may not start until the patient's hematologic, liver and renal functions have been re-confirmed as eligible according to Section 3.1 by the Investigator. Therefore, the regorafenib cycle starts on the day that treatment begins. If liver function toxicities are present, patient may be rechecked weekly for 2 additional weeks. Those patients with persistent liver function toxicities after this time will come off study, but will be followed until resolution.

CONFIDENTIAL

STUDY DEVICE: SIR-Spheres®

SCRI INNOVATIONS STUDY NUMBER: GI 189

DATE OF ORIGINAL PROTOCOL: 16 December 2013

Date of Amendment #1: 15 April 2014

Version 2.0

- Physical examination, weight, and vital signs
- BP
- ECOG PS
- AE assessment
- Concomitant medication review
- CBC
- CMP
- PT/PTT/INR (for patients receiving Coumadin therapy)
- CEA tumor marker
- Biomarker blood sample collection (Day 30 following SIR-Spheres treatment only)

7.4.5 Cycle 2, Day 8 and 15

- Physical examination, weight, and vital signs
- BP
- ECOG PS
- AE assessment
- Concomitant medication review
- CBC
- CMP
- PT/PTT/INR (for patients receiving Coumadin therapy)

7.4.6 Cycle 2, Day 22

- BP

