7.4.7 Cycle 3 and Beyond, Day 1 (± 72 hours)

- Physical examination, weight, and vital signs
- BP
- ECOG PS
- AE assessment
- Concomitant medication review
- CBC

CONFIDENTIAL

STUDY DEVICE: SIR-Spheres®

SCRI INNOVATIONS STUDY NUMBER: GI 189

DATE OF ORIGINAL PROTOCOL: 16 December 2013

Date of Amendment #1: 15 April 2014

Version 2.0

- CMP
- PT/PTT/INR (for patients receiving Coumadin therapy)
- CEA tumor marker

7.4.8 Cycle 3, Day 8

- BP

7.4.9 Cycle 3 and Beyond, Day 15

- PT/PTT/INR (for patients receiving Coumadin therapy)

7.5 Response Assessment Week 6 and Week 12 after SIR-Spheres, and then every 8 Weeks

Patients will be reassessed for response according to RECIST v1.1 (Appendix C) at Weeks 6 and 12 after SIR-Spheres with CT scans in both cohorts. After completing SIR-Spheres and 2 cycles of regorafenib patients may continue regorafenib treatment alone, if tumor response is stable or better. Patients continuing treatment after Week 12 will have response re-assessed at 8-week intervals (± 1 week). Patients with progressive disease (PD) or unacceptable toxicity will be discontinued from the study.

The following assessment will be performed:

- CT scan of chest, abdomen, and pelvis. If CT chest is normal at baseline this does not have to be repeated with each restaging unless there is a clinical reason to do so. If a CT scan is not possible, then an MRI may be used.

As noted above in the Day 1 assessments for all cycles, CEA tumor markers must be assessed on Day 1 of each cycle and at the End-of-Treatment visit.

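### As headed, Protocol 7.3.7 repeats the post-SIR-Spheres eligibility and off-study rule at every Cohort 1 cycle from Cycle 3 on, while Cohort 2 has it once

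*Protocol*

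**What the plan says.** For Cohort 1, the rule stands under the heading "7.3.7 Cycle 3 and Beyond, Day 1". Regorafenib may not start until hematologic, liver and renal function have been "reconfirmed as eligible according to the Section 3.1 by the Investigator". If liver function toxicities are present, the patient may be rechecked weekly for two more weeks, and then: "Those patients with persistent liver function toxicities after this time will come off study". No grade is attached to those toxicities, and nothing in the paragraph limits it to Cycle 3.

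For Cohort 2, the same paragraph stands in 7.4.4, headed for Cycle 2 Day 1 alone, with function to be "re-confirmed as eligible according to Section 3.1 by the Investigator". The later-cycle section, "7.4.7 Cycle 3 and Beyond, Day 1", is a list of assessments with no eligibility bar and no off-study rule.

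The schedules follow the same pattern. In Appendix A, footnote f is attached to the metabolic panel in the Day 1 column for Cycle 3 and beyond. In Appendix B it is attached only at Cycle 2 Day 1.

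Dose changes for liver tests during regorafenib are set separately, in Protocol Table 3 (Section 6.2.1), for both cohorts.

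**The concern.** The study is described as comparing the safety of two treatment sequences. Protocol 10.4.4 summarizes adverse events leading to discontinuation by cohort, and the SAP plans tables of regorafenib exposure, dose modifications with reasons, and treatment discontinuations with reasons. If sites apply an eligibility bar and an off-study rule at every later cycle in one cohort only, holds, exposure and discontinuations for liver toxicity can differ because of the rule and not because of the sequence. With 25 patients per cohort, a few such cases could be read as a sequence effect.

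The timing adds some weight. Section 8.1.3 puts the typical onset of radioembolization-induced liver disease, which it calls rare, at about 4 to 8 weeks after treatment. The second regorafenib Day 1 after SIR-Spheres falls at weeks 6 to 8, and that is the first visit at which the two cohorts' rules part.

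**Working it through.** The plan gives no figure on this point, so the check compares the texts and counts visits.

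**1. Where the rule applies, as headed**

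| Regorafenib Day 1 after SIR-Spheres | Cohort 1 | Cohort 2 |
|---|---|---|
| First | Cycle 3: rule applies (7.3.7) | Cycle 2: rule applies (7.4.4) |
| Second | Cycle 4: rule applies (7.3.7) | Cycle 3: no rule (7.4.7) |
| Third | Cycle 5: rule applies (7.3.7) | Cycle 4: no rule (7.4.7) |

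**2. Number of checks through the Week 12 restaging**

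Inputs: regorafenib starts or restarts r weeks after SIR-Spheres, with r from 2 to 4 (Section 10.1); cycles last 28 days, that is 4 weeks. With no further delay, the Day 1 visits fall at weeks r, r + 4, r + 8 and so on.

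- r = 2: weeks 2, 6, 10 (next 14)
- r = 3: weeks 3, 7, 11 (next 15)
- r = 4: weeks 4, 8, 12 (next 16)

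There are three visits by Week 12 for every r. As headed, the rule falls on 3 of 3 in Cohort 1 and 1 of 3 in Cohort 2. If it is limited to the first dose after SIR-Spheres, it falls on 1 of 3 in both.

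**3. What the rest of the protocol says about intent**

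- Section 5.1 ties the two extra weeks of rechecks to the rest period after SIR-Spheres, before regorafenib begins.
- Figure 1 stars only Cycle 3 in Cohort 1 and Cycle 2 in Cohort 2. The Cohort 1 note speaks of restarting the drug.
- Footnote f refers to toxicity found after the two-week rest. Appendix A speaks of reinitiation, and Appendix B names Cycle 2 Day 1.
- The list under the 7.3.7 heading contains an item that can happen only once: "Biomarker blood sample collection (Day 30 (pre-dose) following SIR-Spheres treatment". Not everything under that heading recurs.

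These agree on a single check. Against them, 7.3.7 also says that the regorafenib cycle begins on the day treatment begins, which reads naturally cycle by cycle, and no words confine the paragraph to Cycle 3.

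**4. What the literal reading changes at a later cycle**

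Take a bilirubin above 1.5 x ULN on Cohort 1 Cycle 4 Day 1, and the same value on Cohort 2 Cycle 3 Day 1. Section 3.1 caps bilirubin at 1.5 x ULN ("unless the patient has Grade 1 bilirubin elevation due to Gilbert's disease" or a similar syndrome), so 7.3.7 holds the Cohort 1 patient. In Cohort 2 only Protocol Table 3 applies.

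- *Baseline Grade 1, now Grade 2.* Reading the table rows as shifts from baseline, row 1 says "Treat on time and check AST, ALT and bilirubin 2x/week for 2 weeks". The Cohort 2 patient is dosed and the Cohort 1 patient is held. The documents do not print the CTCAE limits. If the lower limit of Grade 2 is 1.5 x ULN or higher, every Grade 2 value is barred by Section 3.1; if it is lower, only values above 1.5 x ULN are.
- *Normal at baseline, now Grade 2.* Row 2 holds the dose in both cohorts, so the hold itself does not differ.
- *Persistence.* Under 7.3.7 the Cohort 1 patient leaves the study after two additional weeks, with no exception. Section 6.2.1 gives no time limit for a hold. Section 6.1, headed for hematologic toxicity, allows three weeks and an exception agreed with the Medical Monitor. This difference is not confined to row 1.

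No rate for any of these groups is given, so no patient count can be derived.

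**The case against.** The best defence is that the document largely answers the point. Regorafenib starts once after SIR-Spheres; two additional weeks can only mean additional to the rest after that procedure; and at Cycle 4 there is no such rest to extend. On this view a site would have to overlook Section 5.1, Figure 1 and footnote f to apply the rule again. This stands as evidence of intent. It does not remove the ambiguity, because the operative section is headed for all later cycles and the Appendix A schedule attaches its footnote to the same column.

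The defence is also right that the consequence is limited. The study tests no hypothesis, is not randomized and enrols its cohorts one after the other. The cohorts already differ by design: Cohort 1 has an extra regorafenib cycle and its own Section 3.1 check before SIR-Spheres (7.3.5). The count of 3 against 1 is a ceiling for patients still on treatment. Treatment stops at progression, restaging begins at Week 6, and the introduction cites a PFS of 1.9 months for regorafenib alone, so many patients may never reach the third visit.

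A reader might infer a second, separate defect: that 7.3.7 and 7.4.4 contradict Protocol Table 3 and that an order of precedence is needed at both. The documents do not support that. At Cohort 2 Cycle 2 Day 1 the patient has had no study regorafenib, so there is no dose to modify and 7.4.4 needs no override. At Cohort 1 Cycle 3 Day 1, a specific condition for restarting naturally prevails over a general toxicity table. The conflict that remains, at Cohort 1 Cycle 4 or later, follows from the heading, depends on CTCAE limits that are not printed, and for row 1 concerns only patients with Grade 1 bilirubin at baseline.

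**Conclusion.** The point holds as a minor inconsistency. As headed, 7.3.7 applies the Section 3.1 re-confirmation, the two-week recheck and the off-study rule on Day 1 of Cycle 3 and every later cycle in Cohort 1; Cohort 2 has them only at its first regorafenib dose after SIR-Spheres. The size is up to 3 checks against 1 through Week 12, assuming 4-week cycles, no further delay and a patient still on treatment. The number of patients held or withdrawn because of it is unknown and probably small.

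A reader might infer that the cohorts were deliberately given different rules, or that the safety comparison is biased by some definite amount. Neither is supported: the surrounding text points to a drafting slip, and no effect on any tabulated outcome can be estimated from the documents. What is established is that a site following 7.3.7 as written would use a hold and withdrawal rule at later cycles that Cohort 2 does not have.

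**What to change.** In 7.3.7, and in Appendix A at footnote f, state that the paragraph applies to Cycle 3 Day 1 only, the first regorafenib dose after SIR-Spheres, matching 7.4.4. Add that from the next cycle on the Section 6 dose-modification tables govern in both cohorts, with Table 3 for liver tests. The Section 3.1 limits, including the Gilbert's exception, stay as they are for the Cycle 3 Day 1 check. Section 7.4.4 needs no change.

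The cost is a sentence or two of protocol text, with no new visit or test. The downside is that Cohort 1 loses a literal repeat of the eligibility check at later cycles. The Day 1 blood count and metabolic panel and the Section 6 rules still apply there, as they do in Cohort 2.

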DATE OF ORIGINAL PROTOCOL: 16 December 2013

Date of Amendment #1: 15 April 2014

Version 2.0

Figure 1 GI 189 Schema

Cohort 1 Regorafenib then SIR-Spheres (n=25)

CYCLE	1			2			3*			4	
WEEK	1	2	3	4	5	6	7	8	9	10	11
Regorafenib 160 mg PO daily	X	X	X	-	-	-	X	X	X	-	X
SIR-Spheres	-	-	-	-	-	X	-	-	-	-	-

Regorafenib - 160 mg orally once daily for Days 1-21 of a 28-day cycle followed by a 1 week washout, then treatment with SIR-Spheres microspheres followed by a 2 week rest*, followed by re-initiation of regorafenib.

*If liver function toxicities are present, patient may be rechecked weekly for 2 additional weeks to allow for appropriate resolution of liver function toxicities prior to re-starting regorafenib.

[figure not shown]
[figure not shown]
NOTE: COHORT 1 ENROLLMENT WILL BE COMPLETED BEFORE COHORT 2 OPENS TO ENROLLMENT

Cohort 2 SIR-Spheres then Regorafenib (n=25)

CYCLE	1			2*			3			4	
WEEK	1	2	3	4	5	6	7	8	9	10	11
SIR-Spheres	X	-	-	-	-	-	-	-	-	-	-
Regorafenib 160 mg PO daily	-	-	X	X	X	-	X	X	X	-	X

Treatment with SIR-Spheres microspheres followed by a 2 week rest* then regorafenib initiated - 160 mg orally once daily for Days 1- 21 of each 28-day cycle.

*If liver function toxicities are present, patient may be rechecked weekly for 2 additional weeks and initiation of regorafenib may be delayed until appropriate resolution of liver function toxicities.

STUDY DEVICE: SIR-Spheres®

DATE OF ORIGINAL PROTOCOL: 16 December 2013

Date of Amendment #1: 15 April 2014

CONFIDENTIAL
SCRI INNOVATIONS STUDY NUMBER: GI 189

Version 2.0

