After SIR-Spheres microspheres have been administered, the patient will be monitored closely during the following 2 week rest period prior to starting regorafenib (see Section 7). If liver function toxicities are present, the patient may be rechecked weekly for 2 additional weeks.

CONFIDENTIAL

STUDY DEVICE: SIR-Spheres®

SCRI INNOVATIONS STUDY NUMBER: GI 189

DATE OF ORIGINAL PROTOCOL: 16 December 2013

Date of Amendment #1: 15 April 2014

Version 2.0

Regorafenib Administration

All patients entering this study will receive regorafenib at a dose of 160 mg orally once daily on Days 1-21 of each 28 day cycle.

Patients will be instructed to take regorafenib with a low-fat breakfast that contains less than 30% fat. Examples of a low-fat breakfast include 2 slices of white toast with 1 tablespoon of low-fat margarine and 1 tablespoon of jelly, and 8 ounces of skim milk (319 calories and 8.2 grams fat); or 1 cup of cereal, 8 ounces of skim milk, 1 slice of toast with jam, apple juice, and 1 cup of coffee or tea (520 calories and 2 grams fat). The time of day for administration of regorafenib should be consistent.

If the patient misses a dose of study drug, the patient should take the dose as soon as possible, but not less than 12 hours before the next dose is due for once daily dosing. If the next dose is due in less than 12 hours for once daily the patient should skip the missed dose and take the next dose as scheduled.

If vomiting occurs after taking the study medication, the patient should be instructed not to retake the dose. Patients should take the next scheduled dose of regorafenib. If vomiting persists the patient should contact the investigator.

No routine prophylactic anti-emetics will be given. However, antiemetics may be administered with nausea and vomiting when they occur, and may be given prophylactically afterwards.

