5.4 Correlative Studies

Blood samples for biomarker testing will be collected from all patients prior to the hepatic angiogram and 99m Tc MAA lung shunt scan, which will be obtained 7-4 days prior to SIR-Spheres treatment (see Section 7.2), on Day 8 after SIR-Spheres treatment, and Day 30 (pre-dose) after SIR-Spheres treatment. Expressions of cytokines and proteins will be measured to explore potential biomarkers that may correlate with clinical outcome.

Cytokine analyses will include, but not be limited to, the following: VEGFA, VEGFC, VEGFD, FGF2, HGF, EGF, PDGF-AA, PDGF-AB/BB, MMP-9, sVEGFR-2, E-selectin, VCAM-1, ICAM-1, MIF, TNF α , IFN- α and - γ , LIF, TGF- α , TGF- β 1, Angiopoietin-2, Endoglin, IGF, Osteopontin, GM-CSF, G-CSF, M-CSF, SCGF- β , SCF, Beta-NGF, PIGF, MCP-1, MCP-3,

CONFIDENTIAL

STUDY DEVICE: SIR-Spheres®

SCRI INNOVATIONS STUDY NUMBER: GI 189

DATE OF ORIGINAL PROTOCOL: 16 December 2013

Date of Amendment #1: 15 April 2014

Version 2.0

RANTES, MIP-1 α , MIP-1 β , MIG, Eotaxin, IP-10, SDF-1 α , GRO- α , CTACK, IL-1 β , IL-2, IL-3, IL-4, IL-5, IL-6, IL-7, IL-8, IL-9, IL-10, IL-12 p40, IL-12 p70, IL-16, CA9 and HIF-1 alpha.

Protein expression in blood samples will be measured by proteomics platform.

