10. STATISTICAL CONSIDERATIONS

10.1 Statistical Design

The safety of two treatment cohorts will be evaluated in this open-label study. The administration sequence of radioembolization with SIR-Spheres and regorafenib is different in the two treatment cohorts. The treatment cohorts are:

Cohort 1 Regorafenib (one cycle) followed by SIR-Spheres followed by re-initiation of regorafenib 2-4 weeks after SIR-Spheres

Cohort 2 SIR-Spheres followed by regorafenib to start 2-4 weeks after SIR-Spheres

Enrollment to Cohort 1 will be completed before Cohort 2 begins enrolling patients. All patients will take regorafenib, orally once-a-day, on Days 1-21 of a 28-day treatment cycle. Twenty-five patients will be treated in each cohort.

Primary Objective

The primary objective of the study is to evaluate the safety of two treatment cohorts combining regorafenib and SIR-Spheres in patients with refractory mCRC with liver metastasis.

Secondary Objectives

The secondary objectives of the study are to evaluate the overall response rate (ORR), progression free survival (PFS), and OS of patients with refractory mCRC when treated with combination SIR-Spheres and regorafenib in the two sequencing cohorts.

Exploratory Objectives

The exploratory objectives will evaluate the status of biomarkers and correlate the clinical outcomes of patients treated in the two SIR-Spheres and regorafenib cohorts.

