Appendix A: Cohort 1 Schedule of Assessments (continued)

- a. Informed Consent must be obtained ≤ 28 days prior to the initiation of study treatment.
- b. The Screening physical examination, update of medical history, ECOG performance status, CBC, CMP, and PT/PTT/INR, and concomitant medication review should be done ≤ 21 days prior to initiation of treatment. However, if these initial examinations are obtained within 72 hours of Cycle 1 Day 1 they do not have to be repeated on Cycle 1 Day 1. Scans to document measurable or evaluable disease (i.e., tumor measurement) and tumor marker (CEA) should be performed ≤ 28 days prior to initiation of treatment.
- c. Physical examinations will include measurements of height (Screening visit only), weight and vital signs (resting heart rate, respiratory rate, oral temperature). Blood pressure should be monitored weekly for the first 6 weeks of regorafenib treatment and then every cycle, or more frequently, if clinically indicated.
- d. Hematology parameters include the following laboratory tests: complete blood count including WBC with 3-part differential (total neutrophil count including bands, lymphocytes, monocytes) hemoglobin, hematocrit and platelets.
- e. CMP must include glucose, BUN, creatinine, sodium, potassium, chloride, calcium, CO₂, ALP, AST, ALT, total bilirubin, total protein, and albumin plus LDH, phosphorus.
- f. If liver function toxicities are present after a 2 week rest, then patients may be rechecked weekly for 2 additional weeks. Reinitiation of regorafenib must be delayed until appropriate resolution of liver function toxicities.
- g. PT/PTT/INR will be monitored in patients receiving Coumadin on Days 1, 8 (Cycle 1 only) and 15 of each treatment cycle.
- h. Biomarker samples (see Section 5.4) will be collected from all patients prior to the hepatic angiogram and ^{99m}Tc MAA lung shunt scan, which will be obtained 7-4 days prior to SIR-Spheres treatment (see Section 7.2) and on Day 8 after SIR-Spheres treatment and Day 30 (pre-dose) after SIR-Spheres treatment.
- i. Serum or urine pregnancy tests are to be conducted in women of childbearing potential within 72 hours of C1D1.

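### The third biomarker sample is labelled Day 30 pre-dose but is scheduled at a visit that falls near Day 15 when regorafenib starts or re-starts on time

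*Protocol*

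**What the plan says.** **The label.** Protocol Section 5.4 sets the two samples after radioembolization as "on Day 8 after SIR-Spheres treatment, and Day 30 (pre-dose) after SIR-Spheres treatment". Footnote h in Appendices A and B gives the same timing, and SAP Section 1.2 repeats it.

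**The visit.** Section 7.3.7 lists the sample at the Day 1 visit of Cycle 3, when Cohort 1 re-starts regorafenib: "Biomarker blood sample collection (Day 30 (pre-dose) following SIR-Spheres treatment". Section 7.4.4 lists it at Cycle 2 Day 1, when Cohort 2 first takes the drug, and leaves out the pre-dose condition: "Biomarker blood sample collection (Day 30 following SIR-Spheres treatment only". Both schedule tables put the entry in the same column, marked as day 30. Neither schedule has a separate Day 30 visit.

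**When that visit occurs.** Section 5.1 says "the patient will be monitored closely during the following 2 week rest period prior to starting regorafenib". The Cohort 2 text under Figure 1 agrees: "Treatment with SIR-Spheres microspheres followed by a 2 week rest* then regorafenib initiated". The extension is described in Appendix A, footnote f: "If liver function toxicities are present after a 2 week rest, then patients may be rechecked weekly for 2 additional weeks". The synopsis and Sections 1.2 and 10.1 give a range with no condition attached, for example "re-initiation of regorafenib 2-4 weeks after SIR-Spheres" for Cohort 1. Sections 7.3.7 and 7.4.4 also hold the start until hematologic, liver and renal function have been re-confirmed.

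**The concern.** On the planned schedule the label and the visit are about two weeks apart, and nothing tells a site which of them governs. With about 5 sites, practice could differ.

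This matters because the exploratory objective (Section 2.3) is to correlate biomarkers with clinical outcomes. The panel in Section 5.4 includes VEGFA, sVEGFR-2 and Angiopoietin-2, and Appendix H describes regorafenib as an inhibitor of the VEGFR2 and TIE2 kinases. A sample taken before regorafenib and one taken after two weeks of daily dosing are therefore not the same measurement. If they share one nominal label, drug effect and SIR-Spheres effect cannot be told apart at that time point. How far a patient's sample departs from the nominal time also depends on whether regorafenib was delayed, and toxicity is one cause of delay.

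**Working it through.** **Inputs**
- Nominal sample day: 30 after SIR-Spheres (Section 5.4, footnote h).
- Sample visit: Day 1 of the regorafenib cycle that follows SIR-Spheres (Sections 7.3.7 and 7.4.4). Day 1 is the day dosing begins.
- Rest: 14 days as planned; 21 or 28 days with one or two weeks of rechecks (Section 5.1, Figure 1 text, Appendix A footnote f).
- Visit window: ±72 hours, or ±3 days (Sections 7.3.7 and 7.4.4).
- Dosing: once daily on cycle Days 1-21 (Section 5.1).
- Assumptions: the SIR-Spheres day is Day 1, dosing starts at the visit, and no doses are missed.

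The week grid for Cohort 1 in Figure 1 is not used. The text beneath it gives the 2-week rest.

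**Formulas**
- Visit day = 1 + rest.
- Doses before a Day 30 sample = 30 − visit day (dosing from the visit day through Day 29), and not below 0.
- Regorafenib cycle day on Day 30 = 30 − visit day + 1.

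| Rest (days) | Visit day | Window | Window includes Day 30 | Doses before a Day 30 sample (over window) | Cycle day on Day 30 |
|---|---|---|---|---|---|
| 14 | 1 + 14 = 15 | 12-18 | No | 30 − 15 = 15 (12-18) | 16 |
| 21 | 1 + 21 = 22 | 19-25 | No | 30 − 22 = 8 (5-11) | 9 |
| 28 | 1 + 28 = 29 | 26-32 | Yes | 30 − 29 = 1 (0-4) | 2 |

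The plan's own figure, Day 30 at the start visit, is reproduced only with a 28-day rest. On time, the visit is 30 − 18 = 12 to 30 − 12 = 18 days early.

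**Other day count.** With SIR-Spheres as Day 0, the visits fall on Days 14 (11-17), 21 (18-24) and 28 (25-31). Again only the 28-day rest reaches Day 30. The on-time dose count becomes 30 − 14 = 16.

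**Other visits.** For an on-time patient, Day 15 of that cycle is 15 + 14 = Day 29, which is close, but Sections 7.3.8 and 7.4.5 list no biomarker draw there. The next cycle's Day 1 is 15 + 28 = Day 43 (window 40-46). No other scheduled draw meets the label.

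**The case against.** The best reply is that *pre-dose* need not mean before regorafenib is started or re-started. Under once-daily dosing it can mean before that day's dose, and the label itself, "Day 30 (pre-dose) after SIR-Spheres treatment", ties the day to SIR-Spheres and not to a cycle. On that reading an on-time patient sampled on Day 30, before the cycle day 16 dose, satisfies the label, and only the placement in the schedules is wrong. This stands. A reader might infer that every on-time patient must break either the day or the pre-dose condition, but the documents do not support that. What is left is that the label and the listed visit cannot both be followed.

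A reader might also infer that the sample is correctly timed only in patients delayed by liver toxicity. That is too broad, because a 1-week delay still misses Day 30. It is also too narrow, because hematologic or renal re-confirmation can hold the start, and the 2-4 week wording carries no condition.

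Three further points stand:
- If all sites draw at the listed visit, every sample precedes post-SIR-Spheres regorafenib and only the day varies. Exposure is mixed only if sites differ, or if draws are made on Day 30 in patients with different start dates.
- Cohort 1 patients are not drug-naive at this visit, since they have already had one cycle.
- The objective is exploratory, with no formal hypothesis testing. The SAP lists no biomarker objective, table or figure, so no specified analysis is affected.

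**Conclusion.** The protocol contradicts itself on when the third biomarker sample is drawn. On the planned 2-week rest the gap is about 15 days, or 12-18 with the visit window, and as many regorafenib doses separate the two possible draws. The visit window reaches Day 30 only after a full 2-week delay. This holds in both cohorts and under either day count, assuming daily dosing from the visit without missed doses.

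If sites resolve the conflict differently, the time point mixes samples taken before and during post-SIR-Spheres regorafenib. If all draw at the visit, sampling day depends on delay; if all draw on Day 30, drug exposure does. Liver toxicity is the main stated reason for delay, but not the only one.

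It would go too far to call the exploratory objective confounded by construction. The pre-angiogram and Day 8 samples are unaffected, and neither document names liver toxicity as an outcome to be correlated with the biomarkers. The point is confined to one exploratory time point, but it is worth correcting because a site cannot follow the plan as written for an on-time patient.

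**What to change.** Reconcile Sections 5.4, 7.3.7 and 7.4.4, footnote h and both schedule tables so that visit and label agree, and carry the result into SAP Section 1.2. The documents do not show which timing was intended, so the sponsor must choose one:
- **Anchor to the visit.** Define the sample as pre-dose at the regorafenib start or re-start visit after SIR-Spheres, and drop Day 30.
- **Anchor to the day.** Keep Day 30 as its own draw in both schedules, and state that pre-dose means before that day's dose.

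In either case, record the actual days since SIR-Spheres and the regorafenib doses taken since SIR-Spheres, and use these instead of the nominal label in any biomarker analysis. If samples have already been drawn, this can still be done wherever dates and dosing were recorded.

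**Cost.** The first option needs only wording, because the visit and draw already exist. Its drawback is that sampling day ranges over about Days 12-32 and still depends on delay, though this is then recorded and can be accounted for. The second option fixes the day but adds a draw outside the listed visits for on-time patients, and leaves regorafenib exposure at sampling dependent on delay. Neither option changes treatment timing.
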